Clinical Trial Prospects (CTP) opt-in data base. A direct mail campaign will be used to compliment regional recruitment from pulmonary rehabilitation programs. CTP will mail recruitment letters to the people in their database with COPD. Screening will occur through an interactive voice response or interactive web response (respondent's choice). Our research staff will follow up with in-person screening as appropriate. We piloted the CTP recruitment strategy and with a single mailing received 31 responses from qualified people.	People with COPD in the CTP database within 25 mile radius: 2,644 Flint, MI

Recruitment from CTP databases will yield people with more moderate forms of the COPD while recruitment from Flint area will help with racial and ethnic diversity in subject recruitment. Both are required to support generalizability of results to the broader population of people with COPD.

Attrition. We expect to retain 70% of subjects at the end of the intervention. Our subjects are older adults with chronic disease and in our experience the most common reasons for attrition will be serious acute exacerbations and other health problems that occur over the 12 months of follow-up.

Power Analysis. The power and sample size were calculated based on the inference of mediators. We adopted the sample size calculation proposed by Vittinghoff¹⁶¹ according to the insight that, under the condition that the intervention and the mediator were correlated, testing the existence of the mediator was equivalent to testing the independent effect of the mediator. The formula of sample size calculation for the linear model was $n = \frac{(Z_\alpha + Z_\beta)^2 \sigma_e^2}{(\gamma \sigma)^2 (1 - \rho^2)}$, where Z_α and Z_β were the quantiles of the standard Gaussian distribution corresponding to the type I and Type II error rates, σ_e^2 was the residual variance, γ was the effect size of the mediator, σ was the

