standard deviation of the mediator, and ρ was the correlation between the intervention and the mediator. We set type I error rate α at 0.05, type II error rate β at 0.2 (power = 0.8), the residual variance at 1, mediator variance at 1, and correlations between intervention and mediator range from 0.1 to 0.5. The effect size γ was determined using Cohen's definition of effect size from small (0.14) to medium (0.39)¹⁶². Evaluating our previous study, we expected to detect small to medium effect size ($\gamma = 0.26$). Therefore, when the correlation between the intervention variable and mediator was 0.3, we required 128 patients to reach 80% power. Because our past experience indicated 30% attrition, we proposed to enroll 183 patients at baseline to provide enough power to infer intermediate variables.

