Data Analysis Plan. Data on all patients who are randomly assigned to Active-Life intervention group and active control group will be analyzed on an intention-to-treat basis. Deviations from randomized allocation will be reported. Summary statistics will be used to characterize the sample distribution at each time period. Proper transformations will be investigated and taken if the sample distributions violate the normality assumption. For **Aim 1** of determining the Active-Life intervention effect on PA and sedentary behavior at 10 weeks, and 3, 6, and 12 months, Analysis of Covariance (ANCOVA) will be used at each time period to adjust for the baseline PA measurements and other baseline covariates.¹⁶³ The dependent variable for the ANCOVA is PA and sedentary behavior described in the Research Design section. The adjusting covariates include age, gender, COPD severity, and variables listed in the "other factors that influence PA" section. The Active-Life intervention is claimed to be effective if the marginal p -value of the intervention variable is < 0.05 . For **Aim 2** of identifying intermediate variables (or mediators) between the Active-Life intervention and PA, we will calculate the average causal mediation effects (ACME).^{164,165} The potential mediators include variables barriers-efficacy for PA, and outcome expectations for PA. The significant non-zero causal mediation effect indicates that the intervention on the PA goes through the mediator. The analysis will be carried out using the R mediation package.¹⁶⁴ Since we anticipate having missing values at 10 weeks, we plan to deal with them via standard multiple imputations. More specifically, we will run mediation analysis on multiple imputed data sets. A confidence interval is used to summarize the ACME. Finally, since the mediation analysis assumes the sequential ignorability assumption^{161,166} we will evaluate this assumption by conducting sensitivity analysis.

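### The stated 80% power at 128 patients belongs to the mediator slope; the ACME test that decides Aim 2 has about 73-75% at the same inputs

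*Combined protocol and SAP*

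**What the plan says.** The Power Analysis sizes the trial on mediation. Its argument carries a proviso: it applies "under the condition that the intervention and the mediator were correlated". Granted that proviso, the plan reasons as follows: "testing the existence of the mediator was equivalent to testing the independent effect of the mediator". It sets type I error 0.05, power 0.8, residual and mediator variances of 1, and a mediator effect of 0.26. It considers "correlations between intervention and mediator range from 0.1 to 0.5". At a correlation of 0.3 it finds that "we required 128 patients to reach 80% power". After allowing for 30% attrition, "we proposed to enroll 183 patients at baseline to provide enough power to infer intermediate variables".

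The Data Analysis Plan then sets the Aim 2 decision rule: "The significant non-zero causal mediation effect indicates that the intervention on the PA goes through the mediator". It adds that "A confidence interval is used to summarize the ACME" and names the R mediation package, but not the type of interval. On missing data it says: "Since we anticipate having missing values at 10 weeks, we plan to deal with them via standard multiple imputations". No power is given for the ACME.

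**The concern.** In linear models the ACME is the product of two estimated coefficients: the effect of the intervention on the mediator, and the effect of the mediator on the outcome given arm. The sample-size formula covers only the second. Stating that intervention and mediator are correlated makes a slope test informative about mediation, but it does not remove the first path's sampling error from an ACME interval. The 80% therefore does not describe the planned test.

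This is the only power figure in the protocol, and the enrolment target of 183 comes from it. A null Aim 2 result would be read against a stated 20% risk of missing a true effect. The formula also points the wrong way when the intervention moves the mediator less than assumed: a smaller correlation lowers the required number, while ACME power falls steeply.

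**Working it through.** **Inputs (Power Analysis; Sample section for 64 per arm).** Alpha 0.05, power 0.80, slope γ = 0.26, correlation ρ = 0.3, mediator variance 1, residual variance 1, attrition 30%. Sidedness is not stated.

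**1. Reproduce the plan's figure.** n = (Zα + Zβ)² σe² / [(γσ)²(1 − ρ²)]

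- Two-sided: (1.960 + 0.842)² / (0.26² × 0.91) = 127.6, so 128. One-sided 0.05 would give 100.5, so 101. Two-sided is therefore inferred.
- Enrolment: 128 / 0.70 = 182.9, so 183.

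Both stated numbers reproduce.

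**2. Power of each path at n = 128, ρ = 0.3 (normal approximation).**

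- Slope: Φ(0.26 × √(128 × 0.91) − 1.960) = 0.801
- Intervention to mediator: Φ(0.3/√0.91 × √128 − 1.960) = 0.945
- Product: 0.801 × 0.945 = 0.757 (0.749 with t distributions)

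**3. Simulate the ACME test.** There are 64 patients per arm. The mediator is 0.6 × arm plus normal error of variance 0.91, which gives variance 1 and ρ = 0.3. The outcome is a direct arm effect plus 0.26 × mediator plus error of variance 1. Cases are complete, with one mediator and no covariates. The ACME counts as significant if its 95% interval excludes zero. Simulation error is at most 0.9 points.

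- Slope t test alone: 78.4-78.8%
- ACME, Monte Carlo (quasi-Bayesian) interval: 73.0-73.8%; type I error 4.6% at γ = 0, ρ = 0.3
- ACME, percentile bootstrap: 73.1-74.6%; type I error 5.2%
- ACME, bias-corrected bootstrap: 80.3%, but type I error 8.3-8.8%

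About 1.5 points of the shortfall come from the formula's normal approximation (80.1% against about 78.5%). The other 4-5 points come from the intervention-to-mediator path.

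**4. Across the plan's range of ρ (n = 128, γ = 0.26).**

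| ρ | Formula n | Slope power, normal | Intervention-to-mediator power, normal | Product | ACME power, simulated |
|---|---|---|---|---|---|
| 0.1 | 118 | 0.833 | 0.205 | 0.171 | about 16% |
| 0.2 | 121 | 0.822 | 0.637 | 0.523 | 48-49% |
| 0.3 | 128 | 0.801 | 0.945 | 0.757 | 73-75% |
| 0.4 | 139 | 0.769 | 0.999 | 0.768 | 75-76% |
| 0.5 | 155 | 0.722 | 1.000 | 0.722 | 70-71% |

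Simulated ACME power peaks at about 76% near ρ = 0.36, so at γ = 0.26 no correlation brings 128 patients to 80%. At ρ of 0.4-0.5 the shortfall is almost wholly slope power (simulated 75.0% and 70.6%), which the plan's own formula already implies.

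**5. What would restore 80% at ρ = 0.3.** About 144 complete cases (simulated 79.8-80.2%), or γ of about 0.286 with 128. At γ = 0.39 power is about 92%.

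**6. If more patients inform the first path.** With the intervention-to-mediator path fitted in 150 or 183 patients and the slope in 128 (an assumption), simulated power is 75.6% or 77.6%.

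**The case against.** The strongest reply is that the plan already says what it powers: it names the mediator's independent effect, states the condition and ties 80% to a correlation of 0.3. That is true of the formula. The section nevertheless ends by claiming adequate power for inference on mediators generally, and the ACME decision rule is never connected to the number.

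The gap is also small beside the uncertainty in the inputs. Raising γ from 0.26 to 0.286 closes it. So would covariates that explain about 17% of the outcome residual variance, since 1 − (0.26/0.286)² = 0.17. That stands as a limit on importance. But the plan names adjusting covariates for Aim 1 only, and its residual variance of 1 may already be net of them. Like for like, the first path costs 4-5 points rather than 5-7; this too is fair.

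The planned analysis uses multiple imputation rather than 128 complete cases, and the documents give no figures to quantify its effect. The scenario in which all 183 inform the first path still stays below 80%.

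The plan does not claim 80% at ρ = 0.2, and the true mediated effect there is a third smaller (0.4 × 0.26 against 0.6 × 0.26), so some loss is expected. The point is that the formula cannot show that loss, and a low correlation is not remote. In Table 2 barriers-efficacy rose from 66.2 (SD 21.9) to 74.6, P = .384. As a rough illustration from ten uncontrolled patients, assuming no change in controls, 8.4/21.9 = 0.38 SD, or ρ near 0.19. Outcome expectations moved more (P = .014).

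**Conclusion.** The concern holds. The 128 and 183 are correctly computed for the slope test, but at the plan's own inputs the test that decides Aim 2 has about 73-75% power, a shortfall of 5-7 points. Type I error is unaffected, and the point is one of accurate reporting rather than a flaw that invalidates the design. The figure assumes a two-sided 5% test, 128 complete cases in equal arms, a Monte Carlo or percentile-bootstrap interval, a single mediator, no covariates, no treatment-mediator interaction, no multiplicity adjustment, and no allowance for delivery in groups of 10. The larger practical risk is a weaker effect of the intervention on the mediator: ACME power at a correlation of 0.2 is about 48-49%.

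**What to change.** In the Power Analysis:

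- Label 80% as the power of the mediator slope, conditional on the intervention-mediator correlation.
- State that 128 complete cases give about 73-75% power for the ACME at γ = 0.26 and ρ = 0.3, before any effect of covariates or multiple imputation.
- Name the interval behind that figure: Monte Carlo or percentile bootstrap, not bias-corrected bootstrap, whose simulated type I error is about 8-9%.
- Tabulate ACME power at n = 128 and γ = 0.26 for ρ from 0.1 to 0.5, noting that at 0.4-0.5 the shortfall is slope power.

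The cost is one reworded paragraph and a five-row table. No patients are added and no analysis changes; the stated power becomes slightly less favourable.

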1. Boosters sessions are scheduled concurrently with the testing sessions at weeks 22 and 34. This is to

minimize the number of trips that subjects make to the laboratory.

2. The booster session is an intervention session that is the same as the intervention sessions during weeks 1-10. These sessions are designed to support people in their efforts to be physically active, to help them remember how to do the exercises and to get them re-energized about being physically active.
3. Each booster sessions takes approximately 2 hours. Since the booster will be combined with testing visits the total time will be 4 hours (booster = 2 and testing = 2).

Measures for Aim 1. The primary dependent variables are the time spent in PA and sedentary behavior. ActivPAL data will be used for hypothesis testing and ActiGraph data will be used to describe the intensity of PA. PA will be measured for 7 consecutive days at each measurement.

A substantial body of literature supports the reliability and validity of the ActivPAL.^{126,127} The *ActivPAL3 accelerometer* will be used to measure the time spent standing/stepping and sitting/lying. The ActivPAL3 accelerometer is a small (15g) rectangular device (53 x 35 x 7 mm) taped to the anterior aspect of the thigh. The sampling frequency is 10 Hz and the recording interval is 0.1 second. The proprietary software classifies free-living activity into time spent lying/sitting, standing and stepping. ActivPAL is waterproofed by wrapping it in a barrier film that does not have to be removed for bathing. First applied in the laboratory, it is then worn 24 hours a day for a 7-day period to capture each measurement, and then removed in the laboratory. This greatly reduces the loss of data that occurs when subjects wear a monitor during waking hours but forget to put it on when they wake up each morning. In our pilot work we have had no missing ActiPAL data. We will report time spent sitting/lying, time spent standing/stepping (separately and combined) and the number of transitions from sitting to standing per day. Time spent standing and stepping and sitting/lying will be used for hypothesis testing (Aim 1).

Complimentary measures of PA.

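### Aim 1 has no stated method for missing outcomes, so its visit-by-visit ANCOVAs rest by default on whoever returns; the sustained-effect estimate could be biased in either direction

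*Combined protocol and SAP*

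**What the plan says.** The Data Analysis Plan opens with "Data on all patients who are randomly assigned to Active-Life intervention group and active control group will be analyzed on an intention-to-treat basis". On the outcomes, Measures for Aim 1 states: "The primary dependent variables are the time spent in PA and sedentary behavior". For Aim 1 the Data Analysis Plan specifies that "Analysis of Covariance (ANCOVA) will be used at each time period to adjust for the baseline PA measurements and other baseline covariates", at 10 weeks and at 3, 6 and 12 months. It says nothing about subjects with no activity data at a visit.

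The one missing-data method appears in the Aim 2 text: "Since we anticipate having missing values at 10 weeks, we plan to deal with them via standard multiple imputations". The next sentence gives its use: "More specifically, we will run mediation analysis on multiple imputed data sets". The only sensitivity analysis in the plan concerns the sequential-ignorability assumption of Aim 2. The Secondary Aim (frailty indicators) has a linear mixed model across all visits, which can use partial follow-up. Aim 1 does not.

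The Attrition paragraph expects to retain 70% at the end of the intervention and says that "the most common reasons for attrition will be serious acute exacerbations and other health problems", occurring across the 12 months of follow-up.

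**The concern.** An ANCOVA of month-12 activity can include only people with month-12 activity unless a rule says otherwise. Without one, each of the four contrasts is estimated on a different, self-selected part of the randomised sample. Each model also ignores activity recorded at the other post-baseline visits, although a person's week-10 or month-3 value says a good deal about a missing month-12 value.

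ANCOVA on observed cases is unbiased if missingness depends only on arm and the baseline covariates in the model. The protocol expects something else: loss from exacerbations and illness arising after baseline, events that its own background section links to falling activity. What is at stake is the Aim 1 hypothesis that the effect is sustained at 3, 6 and 12 months, since those are the visits with no missing-data provision.

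**Working it through.** 1. **The plan's own loss figure.** Inputs from Power Analysis: two-sided alpha 0.05 (sidedness is not stated, but two-sided reproduces the result), power 0.80, mediator effect 0.26, intervention-mediator correlation 0.3, residual and mediator variances 1.
   - n = (1.960 + 0.842)² / (0.26² × (1 − 0.3²)) = 7.849 / 0.0615 = 127.6, rounded up to 128. This matches.
   - Enrolment: 128 / 0.70 = 182.9, rounded up to 183. The Timetable agrees (40 + 50 + 50 + 43 = 183).
   - Expected without outcome data: 183 − 128 = 55, or 30%.

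2. **Timing of loss.** The Attrition paragraph puts 30% loss at the end of the intervention, with health-related loss over follow-up. Power Analysis uses 30% as the single overall figure. The Sample paragraph allows up to 250 recruits for 128 studied, which would be 1 − 128/250 = 49% loss if all were randomised. The number left at month 12 is therefore not fixed by the documents and may be below 128.

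3. **Who has interim data.** Table 5 measures activity at baseline, week 10 and months 3, 6 and 12. A person lost before week 10 has baseline activity only. If month-12 retention were 60% (an assumption), 30 of every 40 losses, or three quarters, would fall in that group.

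4. **Does direction depend on who leaves?** Simulation, assumptions: 92 per arm, SD of change 78 min/day (the pilot value), within-person correlation 0.6, true month-12 effect 48, 30% lost, all after week 10.

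| Dropout mechanism | Observed-case ANCOVA | Imputation using week 10 |
|---|---|---|
| Random | 47.8 | 47.8 |
| Poor responders leave both arms equally | 47.7 | 48.1 |
| Poor responders leave Active-Life only | 54.1 | 48.0 |
| Good responders leave Active-Life only | 42.0 | 48.2 |

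5. **With the protocol's timing of loss.** Assumptions: 92 per arm, SD 78, correlation 0.6, true month-12 effect 25 min/day, 30% lost before week 10, retention falling to a little under 60% by month 12. Selective loss is tied to last observed change, at log-odds 0.8 to 1.2 per SD. Where early loss is selective, it is tied to the unseen week-10 change.

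| Dropout mechanism | Observed-case ANCOVA | All-visit analysis |
|---|---|---|
| Early loss random; later loss selective in Active-Life only | about 28 to 30 | about 25 |
| Early and later loss selective in Active-Life only | 32 to 35 | 30 to 31 |
| Same mechanism in both arms | within 1 of 25 | within about 1 of 25 |

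   The standard error of the all-visit estimate was within about 3% of the ANCOVA's in most scenarios, and at worst about 10% larger.

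**The case against.** The plan never calls for a complete-case analysis. A reader might infer that dropping patients was a deliberate choice; the documents show only silence, and the exclusion is what a per-visit ANCOVA does by default. A generous reader could also extend the 10-week imputation to 10-week activity in Aim 1. That is arguable, but it does not reach months 3, 6 and 12. Intention to treat can also be read narrowly as analysing people in the arm assigned, which fits the adjacent promise to report deviations from allocation. Even so, the opening sentence speaks of data on all randomised patients, and a rule for those without outcomes is still needed.

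A stronger reading would be that the analysis will overstate the sustained effect. The documents do not support that. Attrition is attributed to illness, with no reference to arm or response. Several features work against differential loss: equal contact time, payment for each data collection visit, the offer of the other programme afterwards, and the message that those who stop being active still matter. Other features leave it possible: subjects are not blinded, disenchantment with assignment is a stated worry, and only Active-Life sets activity goals and teaches how to stay active through an exacerbation. Neither the presence nor the sign of a bias can be settled from the text.

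It is also tempting to say that interim data would correct the problem. Step 3 shows why that holds only in part: most expected dropouts may have no post-baseline activity at all. Nor is interim activity wasted, since each visit has its own ANCOVA. The point is that no visit's model borrows from the others.

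**Conclusion.** The omission is clear from the text: there is no missing-data method for Aim 1 at months 3, 6 and 12, and at best an implied one at week 10, in a trial that expects about 55 of 183 patients to be lost by the end of the intervention. The consequence is conditional. If the same dropout mechanism acts in both arms, bias is under about 1 min/day on a true 25. If later loss is selective in Active-Life only and early loss is random, the observed-case estimate is about 3 to 5 min/day too high; if good responders leave instead, it is too low. If loss before week 10 is also selective, the observed-case estimate is about 7 to 10 too high, and an all-visit analysis is still about 5 to 6 too high.

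These sizes rest on the assumed effect, correlation, retention and strength of selection. They show what could happen and do not predict it. The change is worth making because it protects the main claim at almost no cost in precision.

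**What to change.** For both activity and sedentary time, replace the four ANCOVAs as the primary Aim 1 analysis with one of the following, and read the arm contrast at each visit from it:

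- one repeated-measures mixed model over all visits for all randomised subjects, with baseline activity as an outcome under a common baseline mean, arm by visit, and unstructured covariance; or
- multiple imputation by arm for all randomised subjects, using activity from all visits and exacerbation count. As Table 5 reads, that count is taken at screening, week 10 and month 12, so only the earlier counts will exist for many dropouts.

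A model limited to subjects with a post-baseline visit would not do, because it omits the same roughly 55 people. Keep the per-visit ANCOVA as a sensitivity analysis. Add a not-at-random sensitivity analysis, for example with dropouts' activity returning to baseline, since no method based on observed visits can address selective loss before week 10. State one expected retention figure for each visit, reconciling Attrition, Power Analysis and Sample.

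The cost is SAP wording and modest programming with methods the plan already uses elsewhere. No extra patients, visits or data are needed. The downside is that the primary analysis then rests on data being missing at random given the observed visits.

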Aim 2. Determine mediating effects of self-efficacy and outcomes expectation on PA and sedentary behavior outcomes of Active-Life. We hypothesize that positive changes in self-efficacy for overcoming barriers to LPA and outcomes expectations for exercise will mediate changes in the time spent in PA and sedentary behavior.

Secondary Aim. Determine short term and sustained effects of Active-Life vs active control on frailty indicators: strength, endurance, balance, walking speed and physical function. The working hypothesis is that the Active-Life group will have significantly higher scores (less frailty) on all frailty indicators after completion of Active-Life compared to the active control group and effects will be sustained at 3, 6 and 12 months.

This research addresses a key issue identified by the 2012 Institute of Medicine report: Living Well With Chronic Disease.³⁹ We will test an intervention to reduce the burden of chronic illness, targeting people with COPD, most of whom have multiple chronic conditions.⁴⁰ The intervention is aimed at physical inactivity, a risk factor for chronic disease. If this intervention is successful in reducing/delaying frailty it could have long reaching economic effects by decreasing health care utilization and the cost of care for people with COPD.

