
Social Cognitive Variables	Δ ^a Standing/Stepping (min./day)	P
Barriers-efficacy for Light PA (baseline)	r = .556	.095
Barriers-efficacy for Light PA (end of intervention)	r = .496	.145
Barriers-efficacy for Light PA (2 mo. follow-up)	r = .515	.128
MOEES (baseline)	r = -.193	.593
MOEES(2 mo. follow-up) ^b	r = -.401	.250

Δ^a = 2-mo. follow-up minus baseline measure; ^bNote data from end of intervention is not available for this measure; BE-PA = barriers-efficacy for physical activity; MOEES = multidimensional outcome expectations for exercise scale.

Figure 3. Timeline for intervention and follow-up boosters

Follow-up = weekly phone coaching for 2 weeks, every other week coaching until 3 months, monthly phone coaching until 6 mo. follow-up.

Summary of Activities

Testing visits	Visit 1	Visit 2	Week 1-10	Week 11	Week 12-21	Week 22	Week 34	Week 62
Screening	X							
Testing visit #1-5		X		X		X	X	X
Activity monitoring (7 days)		X		X		X	X	X
Structured intervention elements			Week 1- 10		Week 11-21	Week 22	Week 34	
Lab-based exercises, with behavioral/ educational program			two visits a week for 8 weeks, then one visit/week for 2 weeks.					
Coaching phone calls (5 minutes)					Total of 8 phone calls during the first 6 months of follow-up.			
Booster session (one full lab-based session)						X*	X*	

Active-Life intervention. Key components are described below and in Table 4. The details of the intervention are documented in a manual for the staff to use, session-by-session, making it easy to implement in a systematic manner (Appendix A section 44.1).

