Secondary Aim. To evaluate the short term and sustained effects of the Active-Life intervention, the linear mixed model (LMM) with a random intercept will be used to model the effect of the intervention. The random intercept in the LMM takes into account that the frailty indicators measured at baseline, 10 weeks; and 3, 6, and 12 months are correlated within the same individual. A number of response variables characterizing the effects of the intervention are considered, based on strength, endurance, physical function, balance, and walking speed. In addition to the binary indicator variable representing intervention or control, the demographic variables such as age, gender, and race will be added as covariates in the LMM to improve the precision of estimation. The intervention is claimed to be statistically significant if the p -value of the intervention variable is < 0.05 .

Strategies to address potential limitations.

Recruitment. We have used our state wide connections to establish a robust plan for subject recruitment. Travel distance is an important predictor of program completion,⁶³ so we will establish regional data collection sites in Grand Blanc, and Flint in addition to Ann Arbor. We require only a small space for training and all equipment is portable so all interventions and data collection can be performed on site. This will reduce the need for subjects to travel long distances for testing.

Retention activities. (a) At enrollment all subjects will be told that if they wish, they can participate in the alternative intervention after completing their assigned intervention and follow-up. This is to minimize subjects' disenchantment based on group assignment and to minimize attrition. We have taken this approach with two previous intervention studies and it dispels subjects' concerns about random assignment to groups. We will not conduct any data collection during the alternative intervention. In our experience a few people will take us up on this offer. (b) We will provide financial incentives for each data collection visit (\$25) and for each 7-days of PA data (\$50), but not for intervention visits because a financial incentive for training would limit generalizability of results. (c) To minimize the loss at follow-up, we will tell subjects that it is just as important that we study those who stop being active as those who continue with their PA.

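### The frailty model pools all visits into one intervention effect, so it does not test sustained benefit; if visit contrasts are added, its random-intercept covariance could mis-size the change-from-baseline tests

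*Combined protocol and SAP*

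**What the plan says.** The Secondary Aim (Specific Aims) hypothesises less frailty after the programme "compared to the active control group and effects will be sustained at 3, 6 and 12 months". For this aim the Data Analysis Plan states that "the linear mixed model (LMM) with a random intercept will be used to model the effect of the intervention". The reason given is dependence among repeated scores from one person, in a sentence that opens: "The random intercept in the LMM takes into account that the frailty indicators measured at baseline, 10 weeks; and 3, 6, and 12 months". Baseline is therefore one of five responses, not a covariate.

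On fixed effects it says: "In addition to the binary indicator variable representing intervention or control, the demographic variables such as age, gender, and race will be added". The decision rule is: "The intervention is claimed to be statistically significant if the p -value of the intervention variable is < 0.05". No visit term, group-by-visit term, visit-specific contrast, serial residual structure or robust standard error is listed.

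The Summary of Activities table puts testing at baseline and weeks 11, 22, 34 and 62. The booster procedure agrees on the middle two: "Boosters sessions are scheduled concurrently with the testing sessions at weeks 22 and 34". On dropout, the Attrition paragraph says "We expect to retain 70% of subjects at the end of the intervention".

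**The concern.** A random intercept with independent residuals imposes one variance and one correlation on every pair of visits, whether 11 or 62 weeks apart. In a disease that the protocol describes as marked by exacerbations and further decline in activity, correlation may well weaken with time. The model would then apply one averaged within-person error to every change from baseline: too much for the short interval and too little for the long one. The 12-month contrast, on which the word sustained rests, would be the anti-conservative one.

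The more basic matter lies in the same paragraph. The model is introduced as the way to evaluate short-term and sustained effects, yet the test described is one coefficient across all visits. The covariance starts to matter only when that gap is repaired, so the two should be settled together.

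**Working it through.** **The plan's own figures.** None is given for the frailty model. The stated sample size belongs to the mediation test and reproduces: (1.960 + 0.842)² / (0.26² × (1 − 0.3²)) = 127.6, so 128; and 128/0.70 = 182.9, so 183.

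**What the documents show about correlation.** From the pilot six-minute walk (Table 2 and the text on frailty, N=10), r = (SD₁² + SD₂² − SD_change²)/(2·SD₁·SD₂):
- baseline to end of intervention: (352² + 285² − 128²)/(2·352·285) = 0.94
- baseline to 2-month follow-up: (352² + 342² − 129²)/(2·352·342) = 0.93
- end of intervention to follow-up: (285² + 342² − 129²)/(2·285·342) = 0.93

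These are flat, but say nothing about week 62.

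**The test as written.** Take equal variances σ² and complete data, and let ρ̄ be the mean correlation over the ten visit pairs. The true variance of a person's five-visit mean is σ²(5 + 20ρ̄)/25 = σ²(1 + 4ρ̄)/5. The random-intercept fit gives the same expression, so the ratio of model to true standard error is 1.000 whatever the decay.

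**What that coefficient estimates.** With complete data and no baseline difference, each visit has weight 1/5. A constant post-baseline effect appears at 4/5 of its size. One present only at week 11 appears at 1/5. One lost only at 12 months still appears at 3/5. Persistence is not tested.

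**Plain group differences at each visit.** True and model variances are both σ² per person, so the ratio is again 1.000.

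**Change from baseline to visit j.** The true variance is 2σ²(1 − ρ₀ⱼ) and the model uses 2σ²(1 − ρ̄). Numbers per arm cancel, so

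ratio = √[(1 − ρ̄)/(1 − ρ₀ⱼ)], and type I error = 2[1 − Φ(1.96 × ratio)].

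The pair lags are 11, 22, 34, 62, 11, 23, 51, 12, 40 and 28 weeks. The decay is assumed. Unless marked, correlation at lag t is ρ₁₁ × (ρ₆₂/ρ₁₁)^((t−11)/51).

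| Correlation at 11 → 62 weeks | ρ̄ | Ratio, week 11 (type I) | Ratio, week 62 (type I) |
|---|---|---|---|
| 0.93 → 0.93 | 0.930 | 1.00 (5.0%) | 1.00 (5.0%) |
| 0.93 → 0.90 | 0.919 | 1.08 (3.5%) | 0.90 (7.8%) |
| 0.93 → 0.88 | 0.912 | 1.12 (2.8%) | 0.86 (9.3%) |
| 0.93 → 0.80 | 0.882 | 1.30 (1.1%) | 0.77 (13.2%) |
| 0.90 → 0.70 | 0.825 | 1.32 (0.9%) | 0.76 (13.4%) |
| 0.90 → 0.70, straight line | 0.828 | 1.31 (1.0%) | 0.76 (13.8%) |
| 0.80 → 0.50 | 0.683 | 1.26 (1.4%) | 0.80 (11.9%) |
| 0.81 → 0.64, as 0.6 + 0.3·exp(−t/30) | 0.729 | 1.19 (2.0%) | 0.87 (9.0%) |

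For example, in the fourth row week 62 gives √(0.118/0.20) = 0.77. A high early correlation is no protection, because only the ratio of the (1 − ρ) values counts.

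**With 30% loss by week 62** (assumed retention 85, 80, 75 and 70% at the four follow-up visits; the plan already expects 70% at the end of the intervention), the pooled coefficient stays at 1.000. Plain differences at week 62 are 0.96 to 0.99, and changes from baseline at week 62 are 0.75 to 0.85.

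**Changing only the covariance.** With correlation matrix R, the pooled coefficient weights visits by R⁻¹1/(1ᵀR⁻¹1). In the table's patterns from 0.93 → 0.88 downward, the post-baseline visits then carry about 0.65 to 0.75 of the weight instead of 0.80, so a constant effect is diluted further.

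**The case against.** The strongest reply is that the plan never produces the intervals at issue. It describes one coefficient and one p-value, correctly sized under this covariance with or without dropout. A reader might infer that the trial's stated frailty test is anti-conservative, or that the plan's 12-month interval is too narrow. The documents support neither: no such interval is specified. That part of the reply stands in full.

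Second, adding group-by-visit terms is not enough to create the problem. Plain between-group differences at each visit are essentially unaffected, and the Secondary Aim speaks of higher scores than the control group, not of change. This also stands, but only in part. With baseline among the responses, group-by-visit coefficients are by default differences in change. The pilot discussion also describes benefit as improved function or slower decline. Constraining the baseline means to be equal does not remove the distortion: the ratios are then about 1.12 to 1.28 at week 11 and 0.78 to 0.86 at week 62.

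Third, the only frailty data in the documents show almost no decay. That is true, but ten patients followed to 2 months after the intervention cannot establish equal correlation to week 62. They do not establish decay either.

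**Conclusion.** The point holds conditionally. The random-intercept model does impose a common correlation, and the plan names no alternative. This does not mis-size the stated p-value; the trouble with that p-value is that it leaves the sustained hypothesis untested.

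Once effects are estimated as change from baseline, as the aim invites, and if correlation falls with lag to the extent assumed, the week-62 standard error is about 13 to 24% too small (type I error about 9 to 14%) and the week-11 one about 12 to 32% too large. Milder decay gives less: 7.8% at week 62 if correlation falls only from 0.93 to 0.90, and exactly 5% with none. The figures also assume equal variances across visits.

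Because this touches a secondary aim, and the primary outcome is analysed by ANCOVA at each time point, it is a minor point.

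**What to change.** Amend the Secondary Aim paragraph of the Data Analysis Plan in one step:

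- Add visit and group-by-visit terms.
- Define the between-group contrasts at 10 weeks and 12 months, saying whether each is a change from baseline and how baseline is handled.
- Replace the random intercept with an unstructured within-person covariance and Kenward-Roger degrees of freedom. If it does not converge, use heterogeneous Toeplitz, or a random intercept with sandwich standard errors.

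Do not change the covariance alone while keeping the pooled coefficient: persistence would remain untested and a constant effect would be diluted further.

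The cost is a few lines of text and no new data. Five visits need up to 15 covariance parameters (5 variances and 10 covariances), which is routine with 128 to 183 patients, and a few degrees of freedom are lost. If correlation does not decay, little is given up.
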